6.1 Screening

Patients will be screened by the investigators at each site in an interval of time between arrival to the emergency room and 12 hours after completion of the coronary angiogram and angioplasty, with an emphasis toward earlier screening. Those patients who meet entry criteria will be approached by the investigators for enrollment. Potential subjects will be provided with an Informed Consent Form in accordance with the local Institutional Review Board. Enrolled subjects will then undergo complete screening for entry criteria (listed below). Where possible, investigators will rely on clinically available laboratory and imaging results; the remaining laboratory and imaging analyses will be ordered and billed to the study account. The timely treatment of patients with STEMI is facilitated by a system of telepaging that alerts the interventional team the need to activate the cardiac catheterization laboratory. The investigators involved in this research at each institute will also be alerted so to facilitate timely screening and enrollment of the subjects. A waiver to obtain authorization by the subjects to access personal health information during screening process will be obtained by the IRB at each center to allow for screening.

STEMI represents 1/3 of all AMI and approximately 10% of ED visits for chest pain. We estimate approximately 120 STEMI yearly at VCU, >150 STEMI yearly at the Washington Hospital Center, and >150 STEMI at the Virginia Cardiovascular Specialists-affiliated hospitals (Chippenham/Johnston Willis Medical Center and Henrico Doctors Hospitals) totaling more than 400 STEMI/year. We propose a conservative enrollment goal of 1 patient/week (total enrollment = 99 weeks). Should enrollment fall behind this goal, we will pursue recruitment at the nearby University of Virginia (Charlottesville, VA) and other community-based centers in Central or Northern Virginia.

6.2 Subject Inclusion and Exclusion Criteria

In order to be eligible for this study, patients must meet ALL the 3 Inclusion criteria and NONE of the Exclusion criteria.

INCLUSION CRITERIA:

- 1) Presentation to the hospital with acute STEMI defined as chest pain (or equivalent) with an onset within 12 hours and ECG evidence of ST segment elevation (>1 mm) in 2 or more anatomically contiguous leads that is new or presumably new
- 2) Coronary angiogram for potential intervention completed within 12 hours of symptom onset, and enrollment in the study within 12 hours of angiogram (max 24 hours from symptom onset)
- 3) Age>21 (NIH standard)

EXCLUSION CRITERIA:

- Inability to give informed consent
- Pregnancy or breastfeeding
- Preexisting congestive heart failure (AHA/ACC class C-D, New York Heart Association III-IV)
- Preexisting severe left ventricular dysfunction (EF<20%)
- Preexisting severe valvular heart disease
- Active infections (acute or chronic)
- Recent (<14 days) or active use of immunosuppressive drugs (including but not limited to high-dose corticosteroids [>1_mg/kg of prednisone equivalent], TNF-α blockers, cyclosporine) not including NSAIDs or corticosteroids used for IV dye allergy only)
- Chronic auto-immune or auto-inflammatory disease (including but not limited to rheumatoid arthritis, systemic lupus erythematosus)
- Known active malignancy of any type, or prior diagnosis in the past 10 years
- Anticipated need for cardiac surgery
- Active cancer (or prior diagnosis of cancer within the past 10 years)
- Neutropenia (absolute neutrophil count<1,800/mm³ [or <1,000/mm³ in African-American patients])
- Severe impairment in renal function (estimated glomerular filtration rate <30 ml/kg*min)
- Allergy to rubber or latex
- Allergy to products derived from Escherichia coli

7) STUDY DESIGN

We designed a multi-center, placebo-controlled, double-blinded randomized study of two different anakinra regimens (100 mg daily or 100 mg twice daily for 14 days). Patients will be enrolled and treated within 12 hours of coronary angiogram/angioplasty and within 24 hours of chest pain onset. A baseline echocardiogram will be ordered within the first 24 hours and repeated at 12 months, as clinically indicated. Biomarkers will be obtained at admission, 72 hours, 14 days, 3, 6 and 12 months.

7.1 Treatment with Anakinra

Anakinra and matching placebo syringes have already been provided by the manufacturer, Swedish Orphan Biovitrum (SOBI, Stockholm, Sweden) to the Investigational Pharmacy at the coordinating center at VCU, where the syringes are stored until ready to be administered to the patient. SOBI has also guaranteed a continuous supply of anakinra and placebo should the current supply expire prior to completion of the trial.

Patients will receive the first dose of anakinra 100 mg or placebo within 12 hours of coronary angiography/angioplasty. The drug will be administered by the nurse and the patients and will be instructed by one of the physicians or pharmacists in the team on how to store and self-administer the drug so they can continue at home twice daily for 14 days. The syringes will be labeled 1 through 28, the patient will be instructed to store them in the fridge and keep them at room temperature for few minutes prior to injection subcutaneously. Proper injection technique will be

taught. A sharp container sufficient to contain all 14 syringes will be given to the patient to dispose the syringes in, and to bring back at the 14-day visit.

One group of patients will receive anakinra 100 mg twice daily for 14 days, a second group will receive anakinra 100 mg alternated with placebo twice daily for 14 days so that anakinra will be given every 24 hours, the third group will receive placebo twice daily for 14 days. The patient will also be educated on expected side effects and need to inform the investigators about any foreseen and unforeseen events.

7.2 Allocation concealment

Anakinra or placebo (vehicle) dispensed in small syringes (1 ml) will be provided by the producer (Swedish Orphan Biovitrum) for subcutaneous injection twice daily. The syringes for anakinra or placebo will be undistinguishable, and labeled with consecutive numbers "1" through "28". The randomization log will be prepared by a consultant outside the institutions involved in the enrollment ([name], University La Sapienza, Rome, Italy) and sent electronically to the director of the Investigational Pharmacy at VCU ([name]). Access to randomization log will be restricted and allowed only on an emergency basis, or as indicated by the Data Safety and Monitoring Board, or at the end of the study including all data collection.

7.3 Patient Compliance with Study Intervention

One goal of the trial is to maximize adherence and retention throughout the study. Adherence will be addressed by count of unused syringes at the 14-day study visit.

7.4 Concomitant Medications

All concomitant medications will be recorded at each clinic visit. Administration of anakinra with medications that affect the immune system (i.e. immunosuppressant) or increase the risk of infection (i.e. cancer chemotherapy) is NOT permitted. If a patient requires treatment with such medications, he/she will not be eligible for inclusion in the study. If a patient already enrolled in the study requires such treatments, the investigational treatment (Anakinra or placebo) will need to be discontinued (see reason for discontinuation).

7.5 Standard Medical Management

Patients in the study will receive guideline-based medical treatments as indicated. Such treatments may include aspirin, P2Y12 inhibitors, β -adrenergic receptor blockers, angiotensin converting enzyme inhibitors or receptor blockers, aldosterone blockers, isosorbide dinitrate, hydralazine, digoxin, and statins.

7.6 Echocardiogram

The patient will undergo a transthoracic echocardiogram, ordered within the first 24 hours, and then again after 12 months, as clinically indicated, to measure left and right ventricular and atrial dimensions, left and right ventricular systolic function, transmitral flow Doppler spectra, mitral and

tricuspidal valve annulus tissue Doppler spectra, ejection time and stroke volume, inferior vena cava, aorta and pulmonary artery diameters and Doppler spectra, according to the recommendations of the American Society of Echocardiography. [16-18] When feasible, results from clinically indicated studies will be used. All images and loops will be acquired in an electronic format and transferred to the VCU Pauley Heart Center for blinded centralized measurements at the end of the study.

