Appendix A: DSMB Chapter for VCU-ART3

Appendix B: Monitoring Plan

Appendix C: Case Report Form and Data Collection Forms

1) PERSONNEL

Name		Role		Institution/ Division			
[name]/PhD			nvestigator	VCU, Cardiology	VCU, Cardiology		
		Co-Principal Investigator		VCU, School of Pharmacy			
[name]		Investigator	\	/irginia Cardiovascular Specialist	s		
[name] [name]		Investigator		VCU, Cardiology			
[name]	Investigator	ator Washington Hospital Center, Cardiology					
[name]		Investigator	Washington Hospital Center, Cardiology				
[name], MS		Research Assistant		VCU, Cardiology			
[name]		Investigationa	al Pharmacy	VCU, Pharmacy	VCU, Pharmacy		
[name]	Adjudicating C	ommittee	VCU, Cardiology	VCU, Cardiology			
[name]	Adjudicating C	ommittee	VCU, Cardiology	VCU, Cardiology			
[name] Event		Adjudicating Committee		VCU, General Medicine			
[name]		DSMB Chair	Un	iversity of Florida, Cardiology			
[name]		DSMB member		VCU, Heart Failure			
[name]		DMSB member		VCU, Infectious disease	VCU, Infectious disease		
[name]		DSMB memb	er	VCU, Cardiology / McGuire VA	١.		
[name]		DSMB memb	er	VCU, General Medicine			
[name]		DSMB coordi	nator	VCU, Johnson Center			
[name]		Consultant		University of Colorado			
[name]		Consultant		Duke University			
[name]		Consultant		Catholic University, Rome, Italy			
[name]		Consultant		Sapienza University, Rome, Italy	y		
[name]		Consultant		VCU, Cardiology / McGuire VA			
[name]		Consultant		VCU, Cardiology			
[name]		Consultant		VCU, Biostatistics			

Abbreviations: DSMB=Data Safety Monitoring Board

2) PROTOCOL SUMMARY

Title: Interleukin-1 Blockade in ST-segment elevation acute myocardial

infarction (STEMI)

Population: 99 patients with STEMI presenting within 12 hours of onset

Site(s): Virginia Commonwealth University, Richmond, VA

> Virginia Cardiovascular Specialists, Richmond VA Washington Hospital Center, Washington DC

Study Duration: 36 months

Description: Phase II clinical trial of Anakinra (standard and higher dose) for 14

> days to quench the acute inflammatory response during STEMI and to prevent adverse cardiac remodeling and heart failure after

STEMI

Objectives: To determine the effects of IL-1 blockade with Anakinra (standard

> and higher dose) on the area-under-the-curve for C-reactive protein (as preferred inflammatory marker in STEMI, and a surrogate for IL-1 activity), the changes in left ventricular dimensions and function,

and the clinical outcomes up to 1 year.

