5.2 Secondary Exploratory Endpoints

Additional endpoints will include parameters measured at echocardiography, as well as biomarkers, and clinical outcomes.

Echocardiography: structural and functional echocardiographic parameters include left and right ventricular dimensions, mass, systolic and diastolic function. These will provide mechanistic insight as to whether the hypothesized changes in the acute inflammatory response will correlate with changes in cardiac dimensions or function. The echocardiogram will be ordered acutely (within 24 hours) and at 1-year follow up as clinically indicated.

Biomarkers: Blood will be collected at each time-point throughout the study (admission, 72 hours [or discharge whichever comes first], 2 weeks, 3, 6 and 12 months) and analyzed for complete blood cell count, metabolic markers (including lipids and lipoproteins, glycemic control and insulin resistance, liver and renal panel, sterols), inflammatory markers (i.e. high sensitivity CRP) and cardiac biomarkers (i.e. NT-proBNP and troponin I). The data will be collected and electronically stored for further analysis at the conclusion of the study. When feasible, results from clinically indicated studies will be used.

Clinical outcomes: Incidence of death (cardiac and non-cardiac), hospitalizations (for HF, for other cardiac causes not related to HF, or for non-cardiac reasons) will be recorded at each time-point throughout the study (discharge, 2 weeks, 3, 6 and 12 months) in every patient, and then once at the end of study, by review of chart and/or telephone interview. The investigators and clinicians caring for the patients will remain blinded to treatment allocation and to the CRP data. Adjudication of events will be performed by an *ad hoc* committee blinded to treatment allocation and to CRP data.

6) ENROLLMENT IN THE STUDY

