7.8 Study Schedule

	Inpatient:	Inpatient: 72 hours	Outpatient Visit 1: 14 days	Outpatient Visit 2: 3 months	Outpatient Visit 3: 6 months	Outpatient Visit 4: 12 months
Screening *	х					
Consent	X					
Clinical assessment **	X	X	X	X	X	X
Investigational therapy	X	X	X			
Echocardiogram	X					X
СВС		X	X			
hs-CRP	X	X	X	X	X	X
Biomarkers	X	X	X	X	X	X

^{*} Pregnancy test will be performed, if indicated

When feasible, results from clinically indicated studies will be used.

^{**}_Clinical assessment includes history and physical, medication reconciliation, and assessment of adverse events

Inpatient samples will be taken upon enrollment, at 72 hours (± 12 hours [or more if patient discharged before 60 hours]).

Samples will be centrifuged and then refrigerated, and shipped with cold pacs within 24 hours to True Health Diagnostics LLC, Richmond, VA. The results will be sent to the PI at VCU and to each center by email or fax.

Outpatient visits will be scheduled at 14 days (± 2 days), 3 months (± 2 weeks), 6 months (± 2 weeks), and 12 months (± 2 weeks).

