	Other:					
	AE review					
Day 5	Drug Dose #1 administered					
//	Drug Dose #2 administered					
	Other:					
	AE review					
Day 6	Drug Dose #1 administered					
//	Drug Dose #2 administered					
	Other:					
	AE review					
Day 7	Drug Dose #1 administered					
	Drug Dose #2 administered					
	Other:					
	AE review					
Day 8	Drug Dose #1 administered					
	Drug Dose #2 administered					
	Other:					
	AE review					
Day 9	Drug Dose #1 administered					
	Drug Dose #2 administered					
	Other:					
	AE review					
Day 10	Drug Dose #1 administered					
	Drug Dose #2 administered					
	Other:					
	AE review					
Day 11	Drug Dose #1 administered					
	Drug Dose #2 administered					
	Other:					
	AE review					
Day 12	Drug Dose #1 administered					
	Drug Dose #2 administered					
	Other:					
	AE review					
Day 13	Drug Dose #1 administered					
/ /	Drug Dose #2 administered					
	Other:		1			
	Blood Draw (14-day HDL)					
	AE review		1			
Day 14	Investigational Drug Reconciliation		1			
//_	Concomitant Rx		1			
			1			
	Other:					

HM20000024 - Interleukin-1 blockade in acute myocardial infarction Blood Draw (12-week HDL) Concomitant Rx 12-week FU __/__/___ AE review Other: Blood Draw (24-week HDL) Concomitant Rx 24-week FU AE review __/__/___ 12-month Echocardiogram ordered Other: Blood Draw (52-week HDL) Concomitant Rx 52-week FU AE review __/__/___ 1-year Echocardiogram Other: Additional Notes: SAEs Reported?Deviations?

	VCU-ART3 Subject # Init	ials	Clinical Site:	vcu / vcs / whc		
	Initial Assessment: STEMI present	ation				
Date	e, time of symptom onset	, ED a	rival,	PCI time		
ECG	G - ST segment elevation (circle all t	hat apply): \	′1 V2 V3 V4 V5	V6 I II III aVF aVL		
[]h	Clinical conditions: (check all that apply) [] hypotension/shock; [] pulmonary edema; [] ventricular arrhythmias [] persistent pain; [] altered mental status					
[]t	cedural data: check all that apply) thrombectomy; [] stent implantati pivalirudin; [] abciximab/eptifibatide; [] as					
[] F [] C	t Medical History: (check all that ap Prior MI; [] Prior PCI; [] Prior CABo Diabetes; [] Hyperlipidemia; [] Cu Chronic Kidney Disease; [] Chronic tes	G; [] Heart rrent Tobac	co user; [] Pe	ripheral Vasc Disease	on	

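### The 12-month echocardiogram is conditional in the text but listed for every patient in the schedule and forms, and no rule covers survivors without one

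*Combined protocol and SAP*

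**What the plan says.** Three places in the text make the 12-month scan conditional:

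- Section 5.2: "The echocardiogram will be ordered acutely (within 24 hours) and at 1-year follow up as clinically indicated".
- Opening of section 7: "A baseline echocardiogram will be ordered within the first 24 hours and repeated at 12 months, as clinically indicated".
- Section 7.6, which first says that the patient will undergo the scan and then adds "and then again after 12 months, as clinically indicated".

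The schedule and forms carry no such condition:

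- The section 7.8 table marks the echocardiogram at the first inpatient time point and at 12 months. Its footnote reads "When feasible, results from clinically indicated studies will be used". That allows clinical scans to be reused; it does not make the scan optional.
- In Appendix C, the cover sheet has the item "12-month Echocardiogram ordered" at 24 weeks and a one-year echocardiogram item at 52 weeks. The 6-month visit form has the repeat scan to be scheduled for the 12-month visit.
- The echo form in Appendix C is only partly legible. It mentions standard clinical care and possible insurance billing, but also says that the study requires a scan.

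The Protocol Summary lists "the changes in left ventricular dimensions and function" among the objectives, and Study Hypothesis (numbered 12.1) includes more favorable remodeling. Section 5.2 classes the echo measures as secondary exploratory endpoints.

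**The concern.** A site cannot tell from these passages whether a patient who is well at 12 months should be scanned. If the text is followed, the 12-month data come from patients who had a clinical reason for a scan. Heart failure is a natural reason, and it is also an outcome the drug is hypothesised to reduce. The patients scanned would then be selected after randomisation on something treatment may affect, and a comparison of scanned patients would no longer be a randomised comparison.

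The analysis sections do not address this. Handling of Withdrawals (10.2) deals with patients whose clinical status cannot be established, not with known survivors who have no scan. Statistical Analysis (12.3) models time and group and gives no rule for a missing echo.

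**Working it through.** The plan states no sample size, power or completion rate for echo, so there is no figure to reproduce. The check asks how far selection could distort the comparison.

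**Inputs**

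- Heart-failure rate h: 30% placebo and 5% anakinra, from the pooled pilot studies described in the background (6 and 1 patients, 40 in total, followed for 3 months).
- Share of heart-failure patients scanned at 12 months, a: assumed 0.9.
- Share of other patients scanned, b: assumed, and varied.

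**Formula**

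Heart-failure share among scanned patients = h·a / (h·a + (1 − h)·b).

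Example with b = 0.6:

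- Placebo: 0.27 / (0.27 + 0.42) = 0.391.
- Anakinra: 0.045 / (0.045 + 0.57) = 0.073.
- Difference: 0.318, against a true difference of 0.30 − 0.05 = 0.25. The ratio is 1.27.

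| b | Placebo share | Anakinra share | Difference | Ratio to 0.25 |
|---|---|---|---|---|
| 0.9 | 0.300 | 0.050 | 0.250 | 1.00 |
| 0.8 | 0.325 | 0.056 | 0.269 | 1.08 |
| 0.6 | 0.391 | 0.073 | 0.318 | 1.27 |
| 0.4 | 0.491 | 0.106 | 0.385 | 1.54 |
| 0.01 | 0.975 | 0.826 | 0.149 | 0.60 |

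The last row shows that the direction can reverse: when almost only heart-failure patients are scanned, the two scanned groups look alike.

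**No treatment effect on heart failure.** Give both arms the average rate, (30% + 5%) / 2 = 17.5%, and scan all heart-failure patients. With 80% of the others scanned, the share is 0.175 / (0.175 + 0.825 × 0.8) = 0.21 in both arms. With 40% scanned, it is 0.35 in both. The scanned group is enriched for heart failure, but equally, so no between-arm difference arises this way.

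**Precision.** The difference detectable with 80% power at the plan's two-sided 0.025 level is (2.241 + 0.842) × √(2/n) SD. That is 0.76 SD with 33 scanned per arm, 0.97 SD with 20 and 1.38 SD with 10. Incomplete scanning costs precision even where it causes no bias.

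**The case against.** A reader might infer that the remodeling data will come from a sicker subset that differs by arm. The documents do not establish that.

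- **No definition of indication.** Nothing says that indication means symptoms or heart failure. With the billing remark on the echo form and the split between standard care and research costs in section 7.9, the phrase may describe routine post-infarction imaging rather than a symptom trigger.
- **The forms prompt a scan for every patient.** Completion could be high, and the bias is then small or absent.
- **Blinding.** Clinicians are blinded to allocation and CRP (5.2), and reading is blinded and central (7.6). This guards against knowing allocation when ordering or measuring. It does not prevent selection through a symptom that treatment changes.
- **A difference by arm needs treatment to change the reason for scanning.** The pilot makes that plausible, but on only 7 heart-failure patients. Deaths and withdrawals before month 12 could instead leave a healthier subset.
- **A suitable model class is already named.** Statistical Analysis specifies a random-effect repeated-measures analysis, which can use patients with only one scan. A rule for missing echoes and information on why a scan is absent are still lacking.

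A reader might also infer that the baseline scan is conditional. Every passage has it ordered within 24 hours, so the point is confined to month 12.

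These objections limit the claim about bias. They do not remove the contradiction or supply the missing rule.

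**Conclusion.** The point holds as an inconsistency with a missing analysis rule, and with a possible bias of unknown size in an exploratory comparison. Under the pilot rates and a 90% scan rate in heart-failure patients, the overstatement of the heart-failure contrast runs from none to about 54% as the scan rate in other patients falls from 90% to 40%. It reverses at very low rates and disappears if treatment does not change the reason for scanning.

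These figures are illustrative. The scan rates are assumptions without a source in the documents. The heart-failure rates are carried from 3 months to 12, and from a once-daily pilot to a trial with a twice-daily arm. The distortion carries over to remodeling only so far as remodeling follows heart-failure status. The CRP AUC primary endpoint and its sample size are untouched, so this is an inexpensive improvement and not a threat to the trial's main result.

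**What to change.** Reconcile 5.2, the opening of 7 and 7.6 with the 7.8 schedule and the Appendix C forms. Either course is workable, and the choice is the sponsor's.

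1. **If the scan is for all survivors:** remove the condition from the three text passages and settle in the section 7.9 cost coverage analysis who pays. The cost is some limited scans that may move from insurer to study budget; central reading is already planned.
2. **If the condition stays:** state in 5.2 that the 12-month echo comparison is descriptive, and report scan completion and reasons for scanning by arm. Fit the random-effect model to all available scans, including patients with a baseline scan only. Use heart-failure status and CRP as auxiliary variables that inform the missing scans. They should not be adjusted for in the treatment contrast, because both may be affected by treatment. Add a sensitivity analysis for missing echoes. The cost is a little more analysis and a more modest remodeling claim.

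Some scans will be missing under the first course too, so the missing-echo rule and completion by arm are worth stating either way.
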